### **Statistical Considerations:**

The primary hypothesis of the study is to show that long term (2 year) functional outcomes for those undergoing Cartiva are no worse than the long term functional outcomes for those undergoing Cheilectomy. The primary outcome is the FAAM – ADL subscore from baseline to 2 years post-surgery. The MCID of FAAM-ADL is 8 units and we assume the SD of the difference in FAAM – ADL from baseline to 2 years post-surgery is near 17 units. To have 80% power in a non-inferiority test under these assumptions, we would need to recruit 57 subjects per group. For those subjects that are lost-to-follow-up or have a subsequent surgery we will impute the missing 2 year follow-up value in two ways: 1) by LOCF (last observation carried forward) and 2) by mean 2 year follow-up value for those in the same surgical group. We will then examine results from both method as a sensitivity analysis of our imputation method. To further assist in ensuring enough patients in each group we will inflate our sample size to 60 per group for a total of 120 patients.

Primary analyses will follow the ITT principle and be based on changes in outcomes from baseline to 2 years follow-up between the two randomized groups. Statistical testing for primary analyses will consist of non-inferiority t-tests between the two groups for each numerical outcome. Secondary analyses will consist of similar non-inferiority t-tests between the two groups but at differing follow-up time points (i.e. 3 months, 6 months, and 12 months). Rates of secondary surgeries will be estimated for each group and 95% Cis will be calculated. Exploratory comparison analyses, including RM-ANOVA and log-rank survival analysis, will be examined as well to see if there were statistical differences in the various outcomes between groups. These analyses methods will be applied similarly to the secondary outcomes as well. For each patient reported outcome measure, we will use the Minimal clinically important difference (MCID) for each measure. As described above, the MCID for the FAAM-ADL subscore is 8 units. The MCID for the FAAM-Sports subscore is 9 units. The MCID for the SF-36 Physical component is estimated at 2 units for patients with lower extremity osteoarthritis conditions. The MCID for the VAS was found to be - 8 mm when evaluating patients with foot pain. Using these values, we will evaluate non-inferiority by comparing the changes from pre-operative results to the results at the described time points. Non-inferiority will be defined as differences that are less than the MCID between the Cartiva and Cheilectomy groups. Furthermore, we will assess whether patient characteristics affected the functional results between the two surgical groups by including a patient characteristic by group interaction into the statistical models.

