#### **Data Safety and Monitoring Plan:**

As seen in previous literature, both the Cheilectomy and Cartiva hemiarthroplasty procedures are relatively low risk. Furthermore, both procedures are indicated for patients with Grade 2 Hallux Rigidus. In the study done by Baumhauer et al, 9% of patients in the Cartiva group required implant removal and revision to a MTP joint fusion. All cases were due to persistent pain following Cartiva implant, with no evidence of significant bone loss or implant wear. Additionally, all cases of revision were successfully revised to an arthrodesis without complication. Additionally, there is an estimated 8-10% revision rate following Cheilectomy, with revision to arthrodesis being the common procedure. For this study, the primary surgeons will use their clinical judgement to determine if a patient will require a revision procedure if they have persistent pain following their initial surgery.

[name], surgical resident in the Department of Orthopedic Surgery will be responsible for the monitoring of this data, under supervision from the PI, [name]. We plan to assess our data and do a primary study evaluation when our enrollment has reached 25% of our stated enrollment goal. Unanticipated problems, adverse events, protocol deviations and violations will be reported to the IRB within 14 days following.

If, at the point of initial evaluation (25% of targeted enrollment), there is a higher than expected complication rate in either treatment arm, the study will be postponed at that time for further evaluation and possible discontinuation.

In the case that our initial evaluation shows negative results and occurs prior to a continuing review, we will contact the IRB with the information and seek to reevaluate or possible discontinue the study. All study team members have completed relevant training materials, are well versed in maintaining clinical integrity and data validity, and will be formally instructed in the

proper application of this protocol. Data/images will be evaluated by the PI, [name], as well as [name] and [name], study team members. This data will be passed to [name], whereupon it will be stored securely as outlined in the Data and Record Keeping section of our protocol."

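### Does the unstated alpha, with only a 5% sample-size allowance, undermine the claimed 80% power?

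*Combined protocol and SAP*

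**What the plan says.** All the inputs are in the Statistical Considerations section. The margin comes from "The MCID of FAAM-ADL is 8 units", and the SD of the change from baseline to 2 years is taken as about 17 units. The result is "To have 80% power in a non-inferiority test under these assumptions, we would need to recruit 57 subjects per group", followed by "we will inflate our sample size to 60 per group for a total of 120 patients". Patients lost to follow-up or re-operated have their 2-year value imputed in two ways, by last observation carried forward and by the mean of their surgical group. The primary analysis follows the ITT principle.

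On testing, the section says "Statistical testing for primary analyses will consist of non-inferiority t-tests between the two groups for each numerical outcome" and "Non-inferiority will be defined as differences that are less than the MCID between the Cartiva and Cheilectomy groups". It gives no alpha for the test. The one interval level it gives belongs to another quantity: "Rates of secondary surgeries will be estimated for each group and 95% Cis will be calculated".

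The Data Safety and Monitoring Plan cites earlier experience: "9% of patients in the Cartiva group required implant removal and revision to a MTP joint fusion" and "there is an estimated 8-10% revision rate following Cheilectomy". Background and Significance also cites a 5% revision rate for Cartiva at 5 years. No rate of loss to follow-up is given anywhere.

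**The concern.** Three things look wrong on a first reading.

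- **Alpha.** A sample size without an alpha cannot be checked as it stands. Many non-inferiority trials use one-sided 0.025, the level that matches a two-sided 95% interval, and 95% is the only interval level in the plan. At that level 57 per group would have about 70% power, not 80%. The choice could also decide the result. With 60 per group and SD 17, the half-width is 5.15 units for a 90% interval and 6.15 for a 95% interval, so an observed Cartiva deficit between about 1.9 and 2.9 units would pass on the first and fail on the second.
- **Allowance.** Going from 57 to 60 covers 5% lost information. Revision alone is cited at about 9%, and re-operated patients are treated as missing at 2 years, before any ordinary loss over two years is counted.
- **Decision rule.** The sentence defining non-inferiority compares a difference with the MCID and names no confidence limit. Taken as a rule on the point estimate, it would declare success half the time when Cartiva is truly 8 units worse.

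**Working it through.** **Inputs.** Margin 8, SD 17, power 80%, 57 and then 60 per group (Statistical Considerations). Revision 9% for Cartiva and 8-10% for cheilectomy (Data Safety and Monitoring Plan), and 5% for Cartiva at 5 years (Background and Significance). Assumed, because not stated: true difference 0, and one-sided alpha of 0.05 or 0.025.

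**Step 1: reproduce 57.** The normal approximation is n = 2(z₁₋α + z₀.₈)² × 17² / 8².

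- One-sided 0.05: 2 × (1.645 + 0.842)² × 289 / 64 = 55.8, so 56.
- One-sided 0.025: 2 × (1.960 + 0.842)² × 289 / 64 = 70.9, so 71.

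For the t-test that the plan names, power comes from the noncentral t with 2n − 2 degrees of freedom and noncentrality 8 / (17 × √(2/n)). At n = 57 the noncentrality is 8 / 3.184 = 2.512.

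| n per group | Power, one-sided 0.05 | Power, one-sided 0.025 |
|---|---|---|
| 56 | 79.7% | 69.4% |
| 57 | 80.3% | 70.2% |
| 60 | 82.1% | 72.5% |
| 72 | 87.8% | 80.1% |

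The smallest n reaching 80% is 57 at one-sided 0.05 and 72 at one-sided 0.025. The plan's figure is reproduced exactly at 0.05 and missed by 15 per group at 0.025.

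**Step 2: the allowance.** 1 − 57/60 = 5.0%. Suppose, as a worst case for information, that every revised patient contributes nothing.

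| Share contributing nothing | Usable n per group | Power, one-sided 0.05 |
|---|---|---|
| 8% | 55.2 | 79.2% |
| 9% | 60 × 0.91 = 54.6 | 78.8% |
| 10% | 54.0 | 78.4% |
| 9% + 5% lost (assumed) | 51.6 | 76.7% |
| 9% + 10% lost (assumed) | 48.6 | 74.5% |
| 9% + 20% lost (assumed) | 42.6 | 69.5% |

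With 5% in the Cartiva arm (57 usable) and 8-10% in the cheilectomy arm (55.2 to 54 usable), power is 79.7% to 79.3%. The revision rates cited in the protocol therefore cost at most 1.6 points against 80%. The last three rows rest on loss rates that are not in the documents.

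**Step 3: the analysis as planned.** The complete-case figures in step 2 are not the planned analysis, which keeps all 60 per group with imputed values. I simulated it at one-sided 0.05 with 9% or 19% missing at random. The assumptions are a correlation of 0.7 between the 1-year and 2-year changes, and the same mean change at both times; neither is in the documents. Nominal power was about 82% under last observation carried forward and about 83% under group-mean imputation. The group-mean figure is partly artificial, because that method understates the variance: at a true deficit of 8 units its type I error was about 7% with 9% missing and about 9% with 19% missing, against the nominal 5%. That is a question about the imputation method, not about the sample size.

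**Step 4: the decision rule.** The section calls for a non-inferiority test with 80% power, carried out by t-test, on the hypothesis that Cartiva is no worse than cheilectomy. A one-sided t-test at 0.05 against a deficit of 8 rejects exactly when the lower limit of the two-sided 90% interval for Cartiva minus cheilectomy lies above −8. Writing that limit into the text gives the same decision as the test already named.

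**The case for a change.** The strongest case for a change is that alpha should be fixed in writing before the data are seen. Between observed deficits of 1.9 and 2.9 units the verdict depends on it, and one sentence would close the gap at no cost in patients. If the sponsor did intend 95% intervals for the primary outcome, the real power is 70-72%. It is also fair to say that a 5% allowance is unexplained in a 2-year surgical trial, and that imputing a value does not restore the information that was lost.

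Part of this stands. Alpha is not written down, and the text would read better if it were. The allowance is not justified, and no loss rate is offered. But nothing in the plan supports 0.025 for the primary test: the 95% intervals are for rates of secondary surgery, and 57 is not the answer at that level. The cited revision rates are literature values rather than this trial's forecast, and they move power by under 2 points. The point-estimate reading of the success sentence works only if the t-test specified in the same section is ignored. Nor is direction missing, since the hypothesis states which procedure must be no worse.

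**Conclusion.** The stated sample size is correct for a one-sided 0.05 non-inferiority t-test with margin 8, SD 17 and true difference 0: 57 per group gives 80.3% and 60 gives 82.1%. Alpha is a missing label that the plan's own numbers identify, and an analyst following the named test would reach the same decision as one given an explicit confidence-limit rule. Revision at the cited rates, counted as total loss of information, leaves power at 78.4-79.7%, which is no reason to alter the design. A material shortfall (74.5% or lower) appears only with 10% or more additional loss, which the documents neither give nor exclude, and only if the affected patients are dropped, which the plan does not do. The conclusion would differ if the sponsor meant one-sided 0.025, but the figure of 57 speaks against that. No change to the plan follows.

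### Missing 2-year FAAM-ADL is imputed in two ways and neither is named as deciding; if the arm-mean version decides, the t-test's standard error is generally too small

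*Combined protocol and SAP*

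**What the plan says.** The Statistical Considerations section makes change in FAAM-ADL from baseline to 2 years the primary outcome, with a margin of 8 units and an assumed SD of change of 17. For "subjects that are lost-to-follow-up or have a subsequent surgery we will impute the missing 2 year follow-up value in two ways", the first way is LOCF and the second is "by mean 2 year follow-up value for those in the same surgical group". It then adds: "We will then examine results from both method as a sensitivity analysis of our imputation method".

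On size: "To have 80% power in a non-inferiority test under these assumptions, we would need to recruit 57 subjects per group", and "To further assist in ensuring enough patients in each group we will inflate our sample size to 60 per group". On analysis: "Primary analyses will follow the ITT principle and be based on changes in outcomes from baseline to 2 years follow-up", and "Statistical testing for primary analyses will consist of non-inferiority t-tests between the two groups for each numerical outcome".

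The Data Safety and Monitoring Plan cites an earlier study in which "9% of patients in the Cartiva group required implant removal and revision to a MTP joint fusion", and an 8-10% revision rate after cheilectomy. Neither rate has a time horizon. Background and Significance gives a different Cartiva figure, 5% at 5 years.

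**The concern.** A sensitivity analysis tests a primary analysis, and here none is named. Both imputations carry the sensitivity label, so when they disagree the trial has no pre-specified verdict on its only powered hypothesis.

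Filling gaps with the arm mean and then running an ordinary t-test counts filled-in values as if they had been observed. If that data set decides, the standard error is generally too small, which makes a false claim of non-inferiority more likely.

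The wording on subsequent surgery has two readings. Either only uncollected 2-year scores are imputed, or any score after a re-operation is treated as missing and replaced. Research Designs and Methods schedules 2-year questionnaires with no exception for re-operated patients, so such scores may well exist. Nor is it said whether LOCF would carry a score from before or after the second operation.

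**Working it through.** **1. The plan's own figure.** Inputs from Statistical Considerations: margin 8, SD 17, power 80%; true difference taken as 0. Alpha is not stated. At one-sided 0.05 the normal formula gives n = 2 × 17² × (1.645 + 0.842)² / 8² = 55.8, so 56 per group. The exact noncentral t gives 57 with 80.3% power. One-sided 0.025 would need 72, and 57 would give 70.2%. One-sided 0.05 is therefore inferred. With 60 per group fully observed, power is 82.1%. The allowance for loss is 1 − 57/60 = 5%.

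**2. Standard error under arm-mean imputation.** Let p be the share imputed, k the 2-year SD divided by the baseline SD, and r their correlation. The plan fills in the 2-year value, not the change, so an imputed patient's change is the observed arm mean minus that patient's own baseline. In units of baseline variance / n, per arm:

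- true variance of the mean change: k²/(1−p) + 1 − 2rk
- variance the t-test reports: (1−p)k² + 1 − 2(1−p)rk

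At k = 1 the ratio of reported to true is exactly 1−p, whatever r is. The SE ratio is then √0.95 = 0.975, √0.90 = 0.949 and √0.80 = 0.894 at 5%, 10% and 20% imputed. A nominal critical value of 1.645 acts like 1.603, 1.560 and 1.471, which gives one-sided error of 5.4%, 5.9% and 7.1%.

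The ratio is below 1 only when k > 2r(1−p)/(2−p). At 10% imputed that means k above 0.9/1.9 = 0.47 for r = 0.5, or above 1.26/1.9 = 0.66 for r = 0.7. The documents give only the SD of change, so k and r have to be varied. Simulated false non-inferiority (60 per arm, true difference −8, SD of change 17, missing completely at random, nominal 5%):

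| Share imputed | k = 1, r = 0.5 | k = 0.6, r = 0.7 | k = 1.3, r = 0.7 |
|---|---|---|---|
| 5% | 5.3% | 4.9% | 5.7% |
| 10% | 5.9% | 4.8% | 6.7% |
| 20% | 7.1% | 4.9% | 8.6% |

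At a nominal one-sided 0.025 with k = 1, the error is 3.1% at 10% imputed and 4.0% at 20%.

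**3. What happens under each deciding rule.** Simulated with baseline, 1-year and 2-year scores, common correlation 0.3, 0.5 or 0.7, the last score always at 1 year, and the 1-year arm difference at 90% of the final one. Ranges run over the three correlations.

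| | 10% imputed | 20% imputed |
|---|---|---|
| Opposite verdicts, equal arms | 5.5-9.6% | 8.1-13.9% |
| Error, arm mean decides | 5.8-6.0% | 6.9-7.0% |
| Error, LOCF decides | 5.2-5.4% | 5.5-5.6% |
| Error, both must pass | 3.8-4.4% | 3.4-4.2% |
| Power, both must pass | 74.7-79.2% | 71.7-77.8% |
| Error, multiple imputation within arm | 4.8-5.1% | 4.7-4.8% |
| Power, multiple imputation within arm | 78.0-79.3% | 74.5-76.4% |

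**4. Subsequent surgery.** If re-operated patients' scores are replaced, a 9% rate alone means 0.09 × 60 = 5.4 patients per arm, against the 3 that the step from 57 to 60 allows. At 5% it is 3 patients. For the effect on the estimate, assume (the documents give no figure) that re-operated patients score 30 points below the rest of their arm. Cartiva at 9% against 8-10% differs by at most 1 point: 0.01 × 30 = 0.3 units, in either direction. Cartiva at 5% against 8-10% differs by 3-5 points: 0.9-1.5 units. The range is 0-1.5 units against the margin of 8.

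**The case against.** The strongest defence is that the plan never says the arm mean decides. It examines both data sets, and a careful analyst would claim non-inferiority only if both agreed, which keeps the error below 5%. This stands in part. A reader might infer that the plan as written inflates the type I error; the documents do not support that, because the inflation needs one particular reading. The requirement that both agree is not written either, and it would bring power below the stated 80%.

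The effect is also small. At the plan's own 5% allowance the excess is about half a point or less with equal SDs, and it vanishes if 2-year scores vary much less than baseline scores. The 10% and 20% shares are assumptions. The disagreement figures assume that every missing patient has a 1-year score; patients lost earlier would carry a 6-week, 3-month or baseline score, and that was not varied.

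On subsequent surgery, a reader might infer that replacing collected scores contradicts the ITT principle. It does not: every patient stays in the randomised arm, and what changes is how a later event enters the outcome. It sits uneasily with collecting 2-year questionnaires from everyone, but it is a choice of estimand. Using all scores has its own drawback, since it credits the later operation to the first procedure and could mask failures. A reader might also infer a bias in favour of Cartiva. The cited rates do not fix its direction, and the 9% comes from a study whose title in the reference list refers to advanced disease, whereas this trial enrols grade 2 only.

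**Conclusion.** The point holds and should be fixed before analysis. Its firmest part needs no simulation: the primary verdict is undefined when the two imputations disagree, and the use of scores after a subsequent surgery is unsettled. The variance problem is conditional on the arm-mean data set deciding. It then adds about one percentage point of error at 10% imputed and two at 20%, with equal SDs and one-sided 0.05. Over k = 0.6-1.3 and r = 0.3-0.7 the error runs from 4.8% to 6.7% at 10% imputed and from 4.9% to 8.6% at 20%. The standard error is therefore generally, not always, too small. The share of patients affected by re-operation by 2 years cannot be read off the documents, and the resulting shift is modest on the assumptions used.

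**What to change.** In Statistical Considerations:

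- Name one primary method with valid variance for missing 2-year values: a mixed model for repeated measures over the FAAM visits collected, or multiple imputation within arm using baseline and interim scores. Keep LOCF and arm-mean imputation as sensitivity analyses at most. List the FAAM visits explicitly: Research Designs and Methods exempts the 2-week visit from questionnaires in one place and has them completed at every visit in another, and the 6-month analysis has no scheduled visit.
- State which estimand is intended for scores after a subsequent surgery, run the other as a sensitivity analysis, and report the already planned secondary-surgery rates with their 95% CIs beside the primary result.
- State the one-sided alpha.
- Describe the 80% power as conditional on about 57 of 60 per arm observed. On observed cases it is about 78% with 54 per arm and 74% with 48.

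The cost is wording, a little more analysis and a slightly less favourable power figure. No new visits or data are needed. Enlarging the trial is optional: holding 80% on observed cases would take 57/0.9 = 63.3, so 64 per arm, at 10% missing, or 57/0.8 = 71.3, so 72, at 20%.

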Joint fusion has become common place in the treatment of advanced stage hallux rigidus, including grade 3 and 4. High fusion rates and patient satisfaction has been proven with fusion procedures in the first MTP joint. However, the loss of motion at the first MTP joint associated with the fusion procedure can interfere with activities such as running and jumping, and can make shoe wear choices difficult. These limitations led to the push for development of a joint replacement procedure, allowing for pain control and continued motion.

The use of silicone-based joint replacement has been met with mixed results, however concerns over the durability leading to implant fracture, osteolysis and difficulty of revision procedures has ultimately limited its use. Ceramic implants were found to have good short-term results, however concerns remain regarding the large amount of subsidence seen in follow up, as well as potential osteolysis. Furthermore, the amount of bone stock remaining following this procedure could make revision procedures quite challenging. Given these mixed results, there remained a significant drive to identify a joint replacement-type procedure with a device that could maintain adequate bone stock, preserve motion and withstand the daily stresses the first MTP joint faces.

This led to the use of the Cartiva implant, a polyvinyl alcohol hydrogel implant. Following extensive safety and wear testing, it was determined that this implant would be well suited for use in patients with hallux rigidus. Indicated for grade 2, 3 and 4 hallux rigidus, the initial study of Cartiva effectiveness compared outcomes of the implant versus arthrodesis. The prospective, randomized control trial evaluated 202 patients, with over 2/3 undergoing the Cartiva procedure. Both short and midterm outcomes were very promising. 5-year revision rates were found to be 5% with no evidence of implant loosening or surrounding bone complication. Additionally, the Cartiva implant was found to be equivalent to the gold standard, arthrodesis, when it came to post-operative patient outcome scores, range of motion and complications.

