#### **Specific Aims/Study Objectives:**

The major hypothesis of this study is that patient outcomes following Cartiva implantation will be non-inferior to those undergoing cheilectomy for patients with grade 2 hallux rigidus. Results will include the FAAM ADL and Sport Subscores, SF-36 scores, Visual analog pain scores and peak active dorsiflexion in the 2 patient populations. Additional results will include secondary

surgeries and adverse events. These will be evaluated pre-operatively and then post operatively at 2 weeks, 6 weeks, 3 months, 1 year and 2 year follow up. The 2 year follow up visit will be the primary end point of the study.

The primary objective of this study will be to evaluate the Cartiva procedure compared to the Cheilectomy with the above stated patient reported outcomes and physical exam measures. These two procedures are both indicated for the patient population selected in this study, however post-surgical results have never been compared to one another in current literature. The secondary objective will be to identify subsets of the study population which may be better suited for one of the two procedures. Through statistical analysis, we will attempt to identify patient variables that may impact the surgical response. This will allow surgeons to appropriately counsel their patients on which procedure they would benefit from.

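### The imputation rule for a subsequent surgery, read across to peak active dorsiflexion, credits motion to fused toes; the distortion is mainly in each arm's mean and SD, and less in the difference between arms

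*Combined protocol and SAP*

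**What the plan says.** All references are to the combined protocol and SAP.

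- **The rule.** Statistical Considerations, for subjects who are lost to follow-up or "have a subsequent surgery we will impute the missing 2 year follow-up value in two ways". The two ways are LOCF and "by mean 2 year follow-up value for those in the same surgical group". Results under both are to be compared as a sensitivity analysis.
- **Its reach.** The same section plans intention-to-treat (ITT) comparisons of change from baseline to 2 years, with a non-inferiority t-test for every numerical outcome, and adds: "These analyses methods will be applied similarly to the secondary outcomes as well".
- **The outcome.** Specific Aims/Study Objectives lists "Visual analog pain scores and peak active dorsiflexion in the 2 patient populations". Research Designs and Methods has it measured by goniometer, standing, before surgery and at the post-operative visits to 2 years. The Data Collection Form has a field for it.
- **What a subsequent surgery usually is.** The Data Safety and Monitoring Plan cites a trial in which 9% of Cartiva patients had the implant removed and the joint fused. For cheilectomy it gives an 8-10% revision rate, "with revision to arthrodesis being the common procedure".
- **What fusion does.** Background and Significance refers to "the loss of motion at the first MTP joint associated with the fusion procedure".

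There is no separate rule for dorsiflexion after a revision, and no statement that readings taken after a revision are kept.

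**The concern.** For a questionnaire score, the value a patient would report after a revision is uncertain, and one can argue about how to impute it. Dorsiflexion is different. The documents themselves give the direction of the truth, since a fused joint has lost motion, and the reading can still be taken at a visit that is already scheduled. The rule replaces that reading with motion from a joint that was not fused: the average of the patient's arm, or the patient's own value from before the fusion.

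Two things follow. First, the planned comparison of LOCF with the arm mean offers no protection. Where the last reading precedes the fusion, both methods err in the same direction, so their agreement shows nothing. Second, replacing a measurable outcome in the randomised arm by a hypothetical one sits badly with the ITT principle that the section adopts.

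At stake is the only physical-examination measure named in the aims, in a trial of an implant whose stated attraction is pain relief with motion kept.

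**Working it through.** **The plan's own figures.** The plan gives no mean, SD or margin for dorsiflexion, so it has no figure to reproduce on this point. Its 57 per group is for FAAM-ADL (margin 8, SD 17, 80% power). It reproduces with a t-based calculation at one-sided 0.05 (power 80.3%), but does not bear on dorsiflexion.

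**Inputs from the documents**
- Group size: 60 per arm.
- Cartiva: 9% revised to fusion (Data Safety and Monitoring Plan); 5% revised by 5 years (Background and Significance).
- Cheilectomy: 8-10% revised, commonly to fusion (Data Safety and Monitoring Plan).

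**Assumptions, not in the documents**
- Mean dorsiflexion in unfused toes, m: 30 to 50 degrees.
- Reading in a fused toe, f: about 0 degrees.
- SD in unfused toes, s: 10 or 15 degrees.
- Every revision is a fusion. This is an upper-end assumption for cheilectomy.

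**Step 1: toes affected.** 60 × 0.08 = 4.8, 60 × 0.09 = 5.4 and 60 × 0.10 = 6.0, so about 5 to 6 per arm. At 5% it is 60 × 0.05 = 3.

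**Step 2: overstatement of one arm's 2-year mean under arm-mean imputation.** With fused share r, this is r × (m − f).
- r = 0.09, f = 0: 0.09 × 30 = 2.7 to 0.09 × 50 = 4.5 degrees.
- If fused toes instead read 10 degrees: 0.09 × 20 = 1.8 to 0.09 × 40 = 3.6 degrees.

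Under LOCF, m is replaced by the last readings of the patients concerned. The error is present only where those readings precede the fusion, and the documents do not allow it to be sized.

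**Step 3: bias in the difference, Cartiva minus cheilectomy.** This is (r_Cartiva − r_cheilectomy) × m, with f = 0. Positive values favour Cartiva.

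| Cartiva | Cheilectomy | m = 30 | m = 50 |
|---|---|---|---|
| 9% | 8% | +0.3 | +0.5 |
| 9% | 9% | 0 | 0 |
| 9% | 10% | −0.3 | −0.5 |
| 5% | 8% | −0.9 | −1.5 |
| 5% | 10% | −1.5 | −2.5 |

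**Step 4: chance imbalance.** If both true rates are 9%, two binomial counts out of 60 differ by 4 or more in about 26% of trials. A gap of 4 toes shifts the reported difference by 4/60 × 30 = 2.0 to 4/60 × 50 = 3.3 degrees, although the average shift over trials is zero.

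**Step 5: SD of the 2-year reading at r = 0.09.** With fused toes at 0, the SD is √(0.91 s² + 0.09 × 0.91 × m²). With arm-mean imputation it is √(0.91 s²).
- m = 30, s = 10: 12.8 against 9.5, ratio 0.74.
- m = 30, s = 15: 16.7 against 14.3, ratio 0.86.
- m = 50, s = 10: 17.2 against 9.5, ratio 0.55.
- m = 50, s = 15: 20.2 against 14.3, ratio 0.71.

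The SD of change also depends on the correlation with baseline, which is not given. The ratios show direction and rough size only.

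**The case against.** **The rule may not reach dorsiflexion.** The imputation sentence follows the FAAM-ADL sample size, and the sentence carrying methods to the secondary outcomes follows the t-tests, RM-ANOVA and log-rank analysis. Missing could also mean only values that were never obtained. This stands as an ambiguity. But the sentence names a subsequent surgery as its own reason to impute, every numerical outcome is to be tested at 2 years, and nothing says that post-revision readings are kept.

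**LOCF is not always wrong.** A toe fused before the 1-year visit may have a post-fusion reading, and the plan does not say that such readings are discarded. This stands. The point holds for the arm mean, and for LOCF only when the last reading precedes the fusion.

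**Not every revision is a fusion.** This stands for cheilectomy, where arthrodesis is described as common, not universal. A reader might infer that all revisions in both arms are fusions; the documents do not say so.

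**The comparison is hardly biased.** At 9% versus 8-10% this stands. A reader might infer that the rule favours the implant by several degrees. That needs a much higher fusion rate after Cartiva, which no section gives. The 5% figure points the other way, and the Background suggests that Cartiva may reduce further procedures.

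**No non-inferiority conclusion is at risk.** This stands too. Margins are given only for patient-reported measures, so the documents do not support a claim that the rule produces a false non-inferiority finding on motion. If cheilectomy had more fusions, the rule would work against Cartiva.

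**Failures are reported elsewhere.** Secondary-surgery rates with 95% CIs and a log-rank analysis are planned, and motion under the original operation is a possible estimand. But the plan does not state that estimand, and it conflicts with the ITT principle that it does state.

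**Conclusion.** The concern holds within limits. On the natural reading of Statistical Considerations, the arm mean always credits motion to a fused toe, and LOCF does so when the last reading precedes the fusion. Comparing the two methods cannot be relied on to reveal it.

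The main effect is on the reported arm means, by about 2.7-4.5 degrees at a 9% fusion share (an upper-end figure for cheilectomy), and on the SD and hence the interval under arm-mean imputation. The expected between-arm bias is small at the cited 9% versus 8-10%, and reaches 0.9-2.5 degrees towards cheilectomy at 5% versus 8-10%. It favours whichever arm has more fusions. These sizes rest on assumed motion of 30-50 degrees unfused and about 0 fused; the documents give neither.

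Because dorsiflexion is a non-primary outcome without a margin, this is a change that should be made, not a threat to the trial's primary conclusion.

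**What to change.** Add to Statistical Considerations:

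1. For peak active dorsiflexion, the goniometer reading at the scheduled 2-year visit is analysed in the randomised arm, including after a subsequent surgery. Imputation applies only when that reading is absent.
2. If the reading is absent after a documented first MTP fusion, neither the arm mean nor a pre-fusion LOCF value is used. The patient's last post-fusion reading is used or, failing that, a prespecified value based on the fused toes measured in the trial, with a sensitivity analysis around it.

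A fixed entry of 0 degrees is a tempting shortcut, but the documents report only a loss of motion and do not say what a fused toe reads on a standing goniometer measurement. It should not be the main rule.

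If the sponsor adopts a general rule of keeping measured post-revision values for all outcomes, item 1 is covered and only item 2 needs adding.

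The cost is a few sentences, since the visit, the measurement and the form field already exist. The downside is that mean motion will look slightly less favourable in each arm and its SD will be larger.
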